Title	Randomised controlled trial to investigate N-nitrosamine formation after meat intake: protocol for Study 1 of the Nitrate INFORMER Studies (Nitrate INFORMER study: I s N itrosamine F ORMation d Ependent on sou R ce)
Investigators	[name] PhD ^{1,2} , [name] PhD ³ , [name] PhD ³ , [name] PhD ¹ , [name] PhD ^{1,2} , [name] ² , [name] ² , [name] PhD ^{1,2} , [name] PhD ⁴ , [name] PhD ¹ , [name] PhD ⁵ , [name] PhD ^{1,2} , [name] PhD ^{1,2} .
Affiliations	¹ Nutrition and Health Innovation Research Institute, School of Medical and Health Sciences, Edith Cowan University, Perth, Australia ² Medical School, The University of Western Australia, Royal Perth Hospital, Perth, Western Australia, Australia ³ School of Biomedical Sciences, University of Western Australia, Royal Perth Hospital, Perth, Western Australia, Australia ⁴ Centre for Integrative Metabolomics and Computational Biology, School of Medical and Health Sciences, Edith Cowan University, Perth, Australia ⁵ Flinders Centre for Epidemiology and Biostatistics, Flinders University, Adelaide, SA, Australia
Hypothesis	Endogenous N -nitrosamine levels will be higher after ingestion of meat with added nitrate compared to meat without added nitrate.
Aims	Primary aim: To investigate nitrate to N -nitrosamine formation after ingestion of meat with and without added nitrate.

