Implementation. Once a participant is deemed eligible and enrolled in the study, the study coordinator will contact the study investigator responsible for randomisation and intervention allocation to obtain the next available envelope and randomly generated intervention sequence.

Blinding

Given the nature of the interventions, participants, and the investigators responsible for delivering the interventions will be unblinded throughout the trial. However, all researchers performing the laboratory analyses and data analyses will be blinded to the interventions that the participants received until after the data analysis has been performed.

Participant timeline

Prior to the first clinic visit, each participant will complete a food frequency questionnaire (FFQ) to assess background habitual diet.

At each clinic visit (**Figure 1**), a baseline urine and faecal stool sample will be collected for measurement of *N*-nitrosamines. Prior to the intervention participants will be instructed to void their bladder into baseline urine collection container. After the first intervention all urine for the subsequent 24-hour period will be collected for measurement of *N*-nitrosamines, nitrate, and nitrite. A faecal stool will be collected for measurement of *N*-nitrosamines, nitrate, and nitrite.

[figure not shown]

Figure 1: Schematic representation of study day timeline

Outcomes *Primary outcomes*

Level of *N*-nitrosamines (*N*-Nitrosodimethylamine, NDMA; *N*-Nitrosomethylethylamine, NMEA; *N*-Nitrosodiethylamine, NDEA; *N*-Nitrosopiperidine, NPIP; *N*-Nitrosomorpholine, NMOR) in urine and faecal stool post intervention.

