Assessments **Urine and faecal stool collection.** A urine sample will be collected at baseline, and from intervention up until 24 hours post-intervention. For the baseline sample, participants will be provided with a sterilized container and instructions to discard the first urine sample of the day and then collect all urine until the intervention which will be brought into the clinic. Participants will be instructed to drink 250 ml water on waking, For the 24-hour urine samples, participants will be provided with sterilized containers and instructions to collect all urine until 24 hours post intervention. Urine aliquots will be frozen at -80°C until analysis. A stool sample will be collected at baseline and for the 24 hour period post the first intervention. Participants will be provided with instructions and a stool sample collection pack (collection bags, cable ties, large zip lock bags, freezer ice blocks and a designated cooler bag for transport). Collected stool samples will be weighed and frozen at -80°C until analysis.

***N*-nitrosamines.** Nitrosamines in the interventions, urine and stool samples will be measured by gas chromatography mass spectrometry (GCMS). Volatile nitrosamines will be extracted with dichloromethane and are well separated by gas chromatography. Identification will be by retention time and unique molecular ions for each of five common nitrosamines (**Table 1**). Quantitation will be made

by using deuterium labelled internal standards, *N*-nitrosodimethylamine-D6; *N*-nitrosodiethylamine D10; *N*-nitrosomorpholine D8 (Cambridge Isotopes) and *N*-nitrosopiperidine D10 (Toronto Research Chemicals). The most commonly detected nitrosamines are NDMA and *N*-Nitrosopiperidine (NPIP). Control experiments in which water stored in the same containers as those used for sample collection and storage will be performed to test for any leaching of volatile nitrosamines.

Table 1: *N*-nitrosamines that will be analysed by GCMS

N -Nitrosamine	Abbreviation	M+ ion (m/z)
N -Nitrosodimethylamine	NDMA	74.05
N -Nitrosomethylethylamine	NMEA	88.06
N -Nitrosodiethylamine	NDEA	102.08
N -Nitrosopiperidine	NPIP	114.08
N -Nitrosomorpholine	NMOR	116.06

Sample size and power

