Sample size is based on a crossover design and the primary outcome of *N*-nitrosamines, specifically *N*-Nitrosodimethylamine (NDMA) in urine. At $\alpha=0.05$, 2 measures per subject (baseline and post) and a correlation of $\rho=0.6$ between measures, 25 participants will provide 80% power to detect a 0.6 SD increase in NDMA concentration. To allow for a 10% withdrawal rate, we plan to recruit 25 participants into the study. A rolling recruitment of participants will be performed until the sample size is reached.

Statistical methods

Statistical analyses will be performed using IBM SPSS Statistics for Windows, version 25 (IBM) and STATA/IC 17.0 (StataCorp LLC). Descriptive statistics of normally distributed continuous variables will be expressed as mean (\pm standard deviation, SD), non-normally distributed continuous variables as median (interquartile range, IQR) and categorical variables as number (proportion, %). Data will be assessed for outliers and normality prior to analysis. Non-normally distributed data will be log transformed if necessary. Treatment effects for outcomes will be obtained using linear mixed models including baseline measurements, treatment order, period, and time (as a categorical variable) as fixed effects. We will also include a treatment X period interaction term to assess for possible treatment-period interactions and we will separately assess for carryover effects with dummy variables to indicate the previous treatment. Treatment effects for outcomes with a single post-intervention measurement will be obtained using linear mixed models including baseline measurements, treatment order, and period as predictors. The subject ID number will be included as a random intercept in each model. An overall 2-sided type-1 error rate of $P<0.05$ will be used to assess statistical significance for all hypothesis testing.

References

1. Lundberg JO and Weitzberg E. NO-synthase independent NO generation in mammals. *Biochem Biophys Res Commun.* 2010;396:39-45.

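### Five nitrosamines in two matrices are listed as primary without ranking, the trial is sized on urine NDMA alone, and no hierarchy, adjustment or success rule says how the 5% error rate applies

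*Combined protocol and SAP*

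**What the plan says.** All places are in the combined protocol and SAP.

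- **Hypothesis.** Nitrosamine "levels will be higher after ingestion of meat with added nitrate compared to meat without added nitrate". This fixes one contrast and a direction, but names no analyte or matrix.
- **Outcomes (Primary outcomes).** The levels of NDMA, NMEA, NDEA, NPIP and NMOR "in urine and faecal stool post intervention". There is no ranking and no sum or composite.
- **Assessments (N-nitrosamines).** "Identification will be by retention time and unique molecular ions for each of five common nitrosamines". The section adds that NDMA and NPIP are the compounds detected most often.
- **Sample size and power.** The basis is the primary outcome, in the singular, narrowed to "Nitrosodimethylamine (NDMA) in urine". The claim is that "25 participants will provide 80% power to detect a 0.6 SD increase in NDMA concentration".
- **Statistical methods.** An "overall 2-sided type-1 error rate of" P<0.05 "will be used to assess statistical significance for all hypothesis testing".

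No section gives a test order, an alpha split, a multiplicity adjustment, or a rule for which primary outcomes must succeed.

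**The concern.** The documents support three counts of primary variables:

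- **Ten:** five compounds in each of two matrices, since each compound is identified separately.
- **Two:** one total per matrix, although no total is defined.
- **One:** urine NDMA, if the sizing paragraph is taken to define the primary outcome.

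The sizing paragraph favours the last reading, but it does not demote the outcomes that the Outcomes section still calls primary, and the testing sentence is not limited to urine NDMA.

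The error rate depends on the success rule. It stays at or below 5% if only urine NDMA is confirmatory, or if every primary outcome must be significant. It exceeds 5% if any one significant primary outcome counts as support. Because none of these rules is written, the choice can be made once results are known. If urine NDMA were null and stool NPIP significant, a reader could not tell whether the hypothesis was supported. The Background says that the trials are meant to inform international guidance on nitrate, so this is worth settling beforehand.

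**Working it through.** **Inputs from the plan.** Two-sided 0.05; five compounds; two matrices; one contrast (Hypothesis); n = 25, a 0.6 SD increase, rho = 0.6 between baseline and post, 80% power, 10% withdrawal (Sample size and power).

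**Assumed inputs.** Equal correlation r between outcomes, from 0 to 0.95, because the documents give none. Any one significant outcome counts as support. The four-outcome case assumes that only NDMA and NPIP can be analysed in each matrix; the documents give no detection rates.

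**Step 1: the plan's own power figure.** For a paired comparison the standardised effect is 0.6/√(2(1 − 0.6)) = 0.671. At n = 25 and two-sided 0.05, the noncentral t gives 0.896. If 0.6 SD is instead in units of the SD of the difference, the effect is 0.600 and power is 0.821. The stated 80% is nearest the second reading, which does not use rho. Other readings give less: with baseline adjustment and independent periods the effect is 0.6/√(2(1 − 0.6²)) = 0.530 and power is 0.721. How the 80% was obtained is a separate question. The first two readings serve below only to show what splitting alpha costs.

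**Step 2: chance of at least one false positive among k outcomes.** With r = 0:

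- either direction, 1 − 0.95^k: k = 2 gives 0.0975, k = 4 gives 0.185, k = 10 gives 0.401;
- hypothesised direction, 1 − 0.975^k: 0.049, 0.096, 0.224.

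With r > 0, and c = 1.96, the either-direction probability is 1 − ∫[Φ((c − √r·g)/√(1 − r)) − Φ((−c − √r·g)/√(1 − r))]^k φ(g) dg. The hypothesised-direction version drops the second Φ term.

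| Outcomes | Direction | r = 0 | 0.3 | 0.5 | 0.8 | 0.95 |
|---|---|---|---|---|---|---|
| 1 | either | 5% | 5% | 5% | 5% | 5% |
| 1 | hypothesised | 2.5% | 2.5% | 2.5% | 2.5% | 2.5% |
| 2 | either | 9.8% | 9.5% | 9.1% | 7.8% | 6.5% |
| 2 | hypothesised | 4.9% | 4.8% | 4.5% | 3.9% | 3.2% |
| 4 | either | 18.5% | 17% | 16% | 11% | 8% |
| 4 | hypothesised | 9.6% | 8.7% | 7.8% | 5.7% | 4.0% |
| 10 | either | 40% | 35% | 29% | 17% | 10% |
| 10 | hypothesised | 22% | 18% | 14% | 9% | 5% |

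A simulation with one-sample t-tests on 25 within-person differences (20,000 replicates) agrees. For ten outcomes in either direction it gives 0.407, 0.293 and 0.101 at r = 0, 0.5 and 0.95.

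**Step 3: power for urine NDMA if alpha is split (Bonferroni, noncentral t).** The first row is the like-for-like reference. Rho = 0.6 is the plan's baseline-post value, taken to apply to the paired comparison.

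| Level per test | Effect 0.671: n = 25 | n = 22 to 23 | n for 80% | Effect 0.600: n = 25 | n = 22 to 23 | n for 80% |
|---|---|---|---|---|---|---|
| 0.05 (one test) | 90% | 85-87% | 20 | 82% | 77-79% | 24 |
| 0.05/2 = 0.025 | 83% | 76-79% | 24 | 73% | 66-68% | 29 |
| 0.05/10 = 0.005 | 61% | 52-55% | 34 | 48% | 40-43% | 41 |

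The 22 to 23 column reflects 25 recruited less 10% withdrawal: 25 × 0.9 = 22.5.

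**The case against.** The strongest reply is that the plan already has one primary test: the sizing paragraph speaks of a single primary outcome, narrows it to urine NDMA, and the Hypothesis fixes the contrast. On that reading there is no multiplicity. This is a fair reading and must be counted. It does not close the gap, because the same document keeps the other analytes and stool under the primary heading and applies its testing sentence to everything.

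Other points stand in part:

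- **The word *overall*.** A reader might infer a promise of family-wise control that the plan then breaks. The sentence may mean only that one threshold is used throughout. It is ambiguous, not a broken promise; but a common per-test threshold leaves multiplicity unaddressed.
- **The 40% figure.** A reader might take this as the trial's error rate. The documents do not support that. It needs ten analysable, independent outcomes and an any-one-wins rule that is not stated. Assessments suggests that fewer compounds will often be detected, and correlation lowers the figure.
- **Direction.** The hypothesis is directional, and for two outcomes the one-direction rate never exceeds 5%, though it exceeds the 2.5% of a single two-sided test.
- **Blinding.** Analysts stay blinded until the analysis is done. This limits choosing outcomes by result during analysis, but not which outcome is put forward at reporting.

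**Conclusion.** The point holds as an unresolved inconsistency between Outcomes and Sample size and power, left open by Statistical methods. Confidence is high for the omission. The size is conditional: it rests on one contrast, a 0.05 test of each listed outcome, any one significant result counting as support, and assumed correlations. Under those conditions the excess over 5% runs from slight (6.5%, two outcomes at correlation 0.95) to large (40%, ten independent outcomes), with ten as the upper bound on the count for one contrast. If urine NDMA is the only primary test the excess is nil. It should be corrected before the data are analysed. The documents do not show that the trial will have an inflated error rate, only that the plan does not exclude it.

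**What to change.** Reconcile Outcomes with Sample size and power, and carry the result into Statistical methods.

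1. **Preferred.** Name urine NDMA, meat with versus without added nitrate, two-sided 0.05, as the single primary test. Alternatively, put it first in a fixed test order in which later tests at 0.05 proceed only while earlier ones are significant.
2. Label the other urine analytes, all stool analytes and the contrasts with the control as secondary. Report them with estimates and confidence intervals, and state either that they are non-confirmatory or how they are adjusted (for example Holm).
3. State whether a total per matrix will be analysed.
4. Say whether *overall* means family-wise control or a common per-test threshold.

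This costs a few lines of text. N, the 0.05 level for urine NDMA, its power and data collection do not change. The downside of a single primary test is that stool or other analytes cannot support a primary claim on their own.

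If the sponsor wants several outcomes to stay primary, state the success rule and the adjustment and restate the power. A fixed order starting with urine NDMA leaves that test untouched. Bonferroni does not: at 25 completers, power falls from about 90% to 61% over ten outcomes and to 83% over two (or from 82% to 48% and 73% if 0.6 is in units of the SD of the difference), and further with withdrawals.
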